## 7. SELECTION AND WITHDRAWAL OF SUBJECTS

Up to 70 subjects will be enrolled to ensure that the required number of subjects for program need receive a full (5+ weeks) course of GC4419, with an assumed proportion of early discontinuations, for any reason, of approximately 10-20%.

### 7.1. Subject Inclusion Criteria

Patients are required to meet the following inclusion criteria before entering the study:

1. Pathologically-confirmed diagnosis of locally advanced squamous cell carcinoma of the head and neck that will be treated with cisplatin plus concurrent IMRT.

*Note: Patients with unknown primary tumors whose treatment plan matches the requirements specified in Inclusion Criteria #2 and #3 below are eligible for the study.*

2. Treatment plan to receive a continuous course of IMRT delivered as single daily fractions of 2.0 to 2.2 Gy with a cumulative radiation dose of 60-72 Gy. Planned radiation fields must include at least 2 oral sites (left and right buccal mucosa, floor of mouth, left and right lateral tongue, soft palate) that each receive a cumulative dose of at least 50 Gy.

*Note: Unavoidable doses of at least 50 Gy, to include entrance, exit, and scatter doses, still constitute planned radiation.*

3. Patients who have had prior surgery are eligible, provided they have fully recovered from surgery, and patients who may have surgery in the future are eligible.
4. Treatment plan to receive standard cisplatin monotherapy administered either every three weeks (100 mg/m^2 for 3 doses) or weekly (40 mg/m^2 for 6-7 doses). The decision on which cisplatin regimen to use in combination with IMRT and GC4419 will be at the discretion of the Investigator.
5. Age 18 years or older
6. Eastern Cooperative Oncology Group (ECOG) performance status ≤ 2
7. Adequate hematologic function as indicated by:
  - Absolute neutrophil counts (ANC) ≥ 1,500/mm^3
  - Hemoglobin (Hgb) ≥ 9.0 g/dL
  - Platelet count ≥ 100,000/mm^3
8. Adequate renal and liver function as indicated by:
  - Serum creatinine acceptable for treatment with cisplatin per institutional guidelines
  - Total bilirubin ≤ 1.5 × upper-normal limit (ULN)
  - Aspartate aminotransferase (AST) and alanine aminotransferase (ALT) ≤ 2.5 × ULN
  - Alkaline phosphatase ≤ 2.5 × ULN
9. Serum pregnancy test negative for women of childbearing potential
10. Males and females must agree to use a highly effective contraception starting prior to the first day of treatment and continuing after the last dose of GC4419 for 30 days (females) or 90 days (males)
11. Properly obtained written informed consent

## 7.2. Subject Exclusion Criteria

Patients will be excluded if they meet any of the following exclusion criteria:

1. Metastatic disease
2. Prior radiotherapy to the region of the study cancer or adjacent anatomical sites or more than 25% of total body marrow-bearing area (potentially interfering with chemo-tolerance)
3. Prior induction chemotherapy or plans for chemotherapy to be administered only sequentially, not concurrently, with IMRT
4. Planned concurrent chemotherapy other than single agent cisplatin
5. Receiving any approved or investigational anti-cancer agent other than those provided for in this study
6. Concurrent participation in another interventional clinical study or use of another investigational agent within 30 days of first dose of GC4419

*Note: Patients who are participating in non-interventional clinical studies (e.g., QOL, imaging, observational, follow-up studies, etc.) are eligible, regardless of the timing of participation.*

7. Inability to eat soft solid food at baseline for reasons other than mouth soreness after surgery or dental procedures
8. Complete reliance on parenteral or gastrointestinal tube-delivered nutrition at baseline

*Note: Patients who have gastrostomy tubes prophylactically placed are eligible. Patients receiving supplemental nutrition through a gastrostomy tube at baseline may be eligible depending on diet.*

9. Malignant tumors other than head and neck cancer (HNC) within the last 5 years, unless treated definitively and with low risk of recurrence in the judgment of the treating Investigator
10. Active infectious disease excluding oral candidiasis
11. Presence of oral mucositis at baseline. Subjects with mouth or throat pain solely due to post-operative effects are eligible, however.
12. Known history of human immunodeficiency virus (HIV) or active hepatitis B/C (patients who have been vaccinated for hepatitis B and do not have a history of infection are eligible)
13. Female patients who are pregnant or breastfeeding
14. Known allergies or intolerance to cisplatin and similar platinum-containing compounds
15. Requirement for concurrent treatment with nitrates or other drugs that may, in the judgment of the treating Investigator, create a risk for a precipitous decrease in blood pressure.
16. Medical history that includes any condition, or requires the use of concomitant medications which, in the Investigator's judgment, are associated with or create a risk of increased carotid sinus sensitivity, symptomatic bradycardia, or syncopal episodes.

## 7.3. Rationale for Patient Population

Patients with locally advanced squamous cell cancer of the head and neck are appropriate candidates for concurrent chemoradiation as standard of care, with single-agent cisplatin perhaps the most widely accepted and widely used standard regimen.

Eligibility will include patients scheduled to receive the prescribed IMRT/cisplatin regimen either as definitive therapy or post-operatively. Both groups may be candidates for IMRT/cisplatin as standard care and the incidence of severe OM is expected to be similar for both groups. In addition, both have been included in the Phase 1 study, GT-001, the randomized Phase 2b study, GT-201 and the randomized Phase 3 study, GTI-4419-301.

Patients with unknown primary tumor whose IMRT/cisplatin treatment plans conform to study requirements will be eligible.

#### **7.4. Screen Failures**

A subject is considered to be a screen failure if the subject signs the informed consent form but withdraws consent or is deemed ineligible before being enrolled to active treatment. The reason why the subject was precluded from the clinical study will be collected. All subjects who sign the informed consent form for this study, including screening failures, will be entered in the IXRS.

#### **7.5. Randomization Failures**

Not applicable.

#### **7.6. Subject Withdrawal Criteria**

In accordance with the Declaration of Helsinki, a subject has the right to withdraw from the study at any time for any reason. The Investigator may also, at his/her discretion, discontinue a subject from participating in this study at any time. Additionally, study treatment may be discontinued for any of the following reasons:

- Adverse Event (AE)
- Medical requirement to administer a contra-indicated medication
- Subject non-compliance
- Subject has a confirmed positive serum pregnancy test
- Discontinuation of the study at the request of the Sponsor

The primary reason for ceasing treatment with GC4419 will be clearly documented in the subject's medical record and recorded on the appropriate CRF page. A subject who permanently discontinues treatment with GC4419 will not be allowed to be retreated.

If a subject discontinues therapy as a result of an AE or serious adverse event (SAE), every attempt should be made to keep the subject in the study and continue to perform the required study-related follow-up and procedures. If this is not possible or acceptable to the subject, the subject may be withdrawn from the study.

Subjects who withdraw consent for further administration of GC4419 should be encouraged to continue and complete their standard treatment with IMRT/cisplatin, and should be encouraged to continue with other study procedures.

If a subject withdraws consent, additional details about the reasons for that decision will be sought and documented.

## 7.7. Study and Site Closure

Both the Sponsor and the Investigator reserve the right to terminate the study at any time. Should this be necessary, both parties will arrange discontinuation procedures. In terminating the study, the Sponsor and the Investigator will assure that adequate consideration is given to the protection of the subjects' interests.

Upon completion of the study, the monitor will conduct the following activities in conjunction with the Investigator or site staff, as appropriate:

- Return of all study data to the Sponsor (as applicable)
- Resolution of all data queries
- Accountability, reconciliation, and arrangements for all unused GC4419
- Review of site study records for completeness
- Shipment of laboratory samples (as applicable)

In addition, the Sponsor reserves the right to temporarily suspend or prematurely discontinue this study either at a single site or at all sites at any time for reasons including, but not limited to, safety or ethical issues or severe non-compliance. If the Sponsor determines such action is needed, the Sponsor will discuss this with the Investigator (including the reasons for taking such action) at that time. When feasible, the Sponsor will provide advance notification to the Investigator of the impending action prior to it taking effect.

The Sponsor will promptly inform all other investigators and/or institutions conducting the study if the study is suspended or terminated for safety reasons and will also inform the regulatory authorities of the suspension or termination of the study and the reason(s) for the action. If required by applicable regulations, the Investigator must inform the IRB/IEC/Research Ethics Board (REB) promptly and provide the reason for the suspension or termination. If the study is prematurely discontinued, all study data must be returned to the Sponsor.

Financial compensation to investigators and/or institutions will be in accordance with the agreement established between the Investigator and the Sponsor.

## **8. GC4419**

### **8.1. Description of GC4419**

#### **8.1.1. GC4419**

GC4419 (Manganese,dichloro[(4aS,13aS,17aS,21aS)-1,2,3,4,4a,5,6,12,13,13a,14,15,16,17,17a,18,19,20,21a-eicosahydro-11,7-nitilo-7H-dibenzo[b,h][1,2,7,10]tetraazacylcoheptadecine-κN5,κN13,κN18,κN21,κN22]-) is a water soluble, highly stable, low molecular weight manganese-containing macrocyclic ligand complex whose activity mimics that of naturally occurring SOD enzymes.

GC4419 is formulated as a clear solution at the following concentration:

- 90 mg GC4419: 9 mg/mL in 26 mM sodium bicarbonate-buffered 0.9 wt. % saline for parenteral administration.

There are no other excipients.

### **8.2. Treatment Assignment**

This is an open-label study.

### **8.3. GC4419 Packaging and Labeling**

GC4419 will be presented in kits of 35 single-use vials, which represent 35 daily doses to be administered IV concurrent with IMRT.

GC4419 is packaged as an 11 mL  $\pm$  0.1mL aliquot in a 10 mL amber glass vial with a S-127 4432/50 gray stopper and a 20 mm red flip-off seal. Each bottle will be labeled with the appropriate language, including the required regulatory text. Further label details will be provided in a separate Pharmacy Manual.

### **8.4. GC4419 Storage**

GC4419 must be stored at 2°C to 8°C at all times until preparation. GC4419 must not be frozen at any time. Temperature excursions up to 25°C or down to 0.1°C for four hours are accepted; however, the Sponsor or its designee must be notified immediately of the temperature excursion to ensure proper oversight.

Once prepared, the IV bags containing GC4419 saline mixtures must be administered to subjects within 24 hours of preparation. The GC4419 Infusion Solution should spend as little time as possible outside refrigerated conditions, not exceeding more than 6 hours at ambient temperature, and must not be frozen at any time. If freezing of the material is evident, that supply must be quarantined per institutional guidelines, and the Sponsor or its designee must be notified immediately.

## **8.5. GC4419 Preparation**

GC4419 will be provided to the study site in single use, sterile, pyrogen-free vials ready for dose preparation. Proper mixing with normal saline is required. Standard aseptic techniques will be used to maintain sterility.

GC4419 will be presented in kits of 35 single-use vials, which represent 35 daily doses to be administered IV concurrent with IMRT.

To prepare daily IV solutions, investigational pharmacists will extract 10 mL from a single vial and add to 250 mL normal saline. Note that there is no extraction of saline (i.e., the infusion solution volume will be 250 mL saline + 10mL volume of GC4419 for a total volume of 260 mL). No additional modifications or adjustments are to be made to the infusion solution.

Further information and preparation details will be provided in a separate Pharmacy Manual.

## **8.6. GC4419 Administration**

GC4419 saline mixture will be administered intravenously at an infusion rate that totals 60 min ( $\pm$  6 min to account for saline overfill) for the total dose assigned. Infusions of GC4419 must be administered using an infusion pump (i.e., not by drip rate). Infusion pump models are not specified and may be per institutional preference/standard.

To facilitate administration of GC4419 according to the study schedule, an indwelling venous access device may be used, at the discretion of the treating Investigator.

IMRT must be initiated as soon as possible upon completion of the GC4419 infusion, but no later than four hours following the end of the infusion.

GC4419 will be given beginning on the first day of radiation and continuing daily, concurrent with each dose of IMRT, to a cumulative radiation dose of approximately 60-72 Gy.

[Table 2](#) outlines the chemoradiation and GC4419 administration schedules. Please note chemotherapy is not required to be administered on the study days listed in [Table 2](#), as long as it follows a weekly or tri-weekly schedule.

If IMRT is not administered on any given day due to a treatment break or unforeseen circumstances, GC4419 should not be administered on that day. Breaks in IMRT will be determined by the subject's treating physician in accordance with standard of care. Subjects should resume GC4419 administration when IMRT resumes. On days when planned doses of both GC4419 and IMRT are not administered (e.g., due to a holiday site closure), GC4419 dosing may be extended along with IMRT to make up the missed dose(s) to a maximum of 35 doses of GC4419. If a fraction of IMRT is not administered for any reason after GC4419 has been administered, that day's GC4419 will count as one of the 35 doses.

**Table 2: Chemoradiation and GC4419 Administration Schedule**  
**Example: 35 Doses of GC4419 (5 days/week over 7 Week Schedule)**

Treatment	Week 1					Week 2					Week 3					Week 4				
	Day 1	Day 2	Day 3	Day 4	Day 5	Day 8	Day 9	Day 10	Day 11	Day 12	Day 15	Day 16	Day 17	Day 18	Day 19	Day 22	Day 23	Day 24	Day 25	Day 26
GC4419 	X	X	X	X	X	X	X	X	X	X	X	X	X	X	X	X	X	X	X	X
Cisplatin  Tri-Weekly Weekly	X															X				
Radiation 	X	X	X	X	X	X	X	X	X	X	X	X	X	X	X	X	X	X	X	X

Treatment	Week 5					Week 6					Week 7				
	Day 29	Day 30	Day 31	Day 32	Day 33	Day 36	Day 37	Day 38	Day 39	Day 40	Day 43	Day 44	Day 45	Day 46	Day 47
GC4419 	X	X	X	X	X	X	X	X	X	X	X	X	X	X	X
Cisplatin  Tri-Weekly Weekly	X										X				
Radiation 	X	X	X	X	X	X	X	X	X	X	X	X	X	X	X

 Intravenous GC4419 is administered by a 60-minute intravenous infusion ( $\pm 6$  min) once a day for the first 35 days of IMRT (Monday through Friday). IMRT must be initiated as soon as possible upon completion of GC4419 infusion, but no later than four hours post GC4419 infusion. On Day 1/Baseline, chemotherapy prehydration and infusion should be administered after GC4419 infusion and IMRT, if possible, to ensure that IMRT is initiated within four hours of the GC4419 infusion stop. If IMRT is not received on any given day due to a treatment break or unforeseen circumstances, GC4419 should not be administered on that day. Subjects should resume GC4419 administration when IMRT resumes. If a subject is scheduled to receive IMRT on a weekend day (e.g., to make-up for a holiday site closure), the Investigator should contact the Medical Monitor for a discussion prior to IMRT administration.

 Cisplatin monotherapy should be administered in a standard q3 weeks regimen ( $100 \text{ mg/m}^2$ ) or weekly regimen ( $40 \text{ mg/m}^2$ ). Anti-emetic prophylaxis and hematopoietic growth factor use should be administered per ASCO guidelines. If institutional guidelines permit, cisplatin may be administered prior to or after the first day of IMRT. On days in which chemotherapy and GC4419 are administered, the administration sequence should be GC4419, IMRT, prehydration, and then cisplatin, if possible, to ensure that IMRT is initiated within four hours of the stop time of GC4419 infusion. Patients treated with induction chemotherapy

prior to concomitant chemoradiation are not eligible for this study, nor are people for whom chemotherapy and radiation are only to be administered sequentially, not in a concurrent regimen.

 Eligible patients will be scheduled to receive a continuous course IMRT delivered in single daily fractions of 2.0 to 2.2 Gy, five days per week (Monday through Friday), with a cumulative radiation dose of 60-72 Gy. Planned radiation treatment fields must include at least two oral sites (buccal mucosa, floor of mouth, tongue, soft palate) that are each planned to receive  $\geq$  50 cumulative Gy.

 The 7th dose of cisplatin will only be administered if the subject is on the 7-dose weekly cisplatin schedule (weekly cisplatin schedule may be 6 or 7 doses, depending on Investigator choice).

## **8.7. GC4419 Accountability and Compliance**

Compliance with GC4419 dosing, including administration details (e.g., volume, start, stop times, etc.) should be documented in the source documents and recorded on the CRF.

The Investigator is responsible for ensuring adequate accountability of all used and unused GC4419. This includes acknowledgment of receipt of each shipment of GC4419 (quantity and condition), subject dispensing records, and quantity of GC4419 returned or destroyed.

Dispensing records will document quantities received from the Sponsor and quantities dispensed to subjects, including container number or lot number, date dispensed, subject identifier number, and the initials of the person dispensing the medication. Any GC4419 that is prepared but not used must also be recorded in the dispensing records.

All GC4419 supplies and associated documentation will be reviewed and verified by the study monitor. Copies of all forms, documenting drug receipt at the study site, drug transportation to satellite sites, and drug return to the Sponsor, together with drug accountability records, will be retained according to the regulations governing record retention.

The Investigator will not allow GC4419 to be given to any patient not included in the study or to any unauthorized person.

## **8.8. GC4419 Handling and Disposal**

All used GC4419 containers are to be retained by the site until notified by the study monitor, who will instruct the site in the disposal and/or destruction of all used GC4419 supplies.

After completion of the study, all unused GC4419 will be inventoried and, if possible, destroyed locally at the site. GC4419 should not be returned directly to the Sponsor unless specifically requested by the Sponsor. The study monitor will instruct the site in the disposal and/or destruction of all used and unused GC4419 supplies. Destruction of any GC4419 should be documented appropriately.

## **8.9. Concomitant Medications**

All concomitant therapies (i.e., prescription and over-the-counter medications) taken by subjects from the date of enrollment through 30 days following the last GC4419, IMRT or cisplatin dose (i.e., whichever occurs last) will be collected in the CRF. Additionally, any concomitant therapies if used to treat any serious or related adverse event will be recorded in the CRF.

Anti-emetic prophylaxis and hematopoietic growth factors should be used per ASCO guidelines ([Hesketh, Kris et al. 2017](#)).

Subjects who withdraw consent for GC4419 should be encouraged to continue and complete standard IMRT/cisplatin treatment and other protocol procedures.

However, if a subject withdraws consent for the study or is removed from the study completely (i.e., the subject is no longer participating in any study procedures or follow-up) no further data should be collected after the date of the subject's study discontinuation.

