### **11.2.2. Collection Period for AEs and SAEs**

Any adverse medical condition or laboratory abnormality with an onset date prior to the date and time the subject received his/her first dose of study drug, GC4419, is considered pre-existing in nature and should be recorded as part of the subject's medical history. An adverse medical condition that begins on or after the first dose of study drug will be considered an adverse event, and will be considered an SAE if it meets serious criteria. AEs and SAEs will be followed for 30 days after the last dose of IMRT, cisplatin, or GC4419 (i.e., whichever occurs last), hereafter referred to as the "30-Day Follow-up Period". Similarly, new events will be reported as AEs/SAEs if the start date is within the 30-Day Follow-up Period. Increases in toxicity grade of pre-existing conditions that occur on or after the first study drug administration are also considered adverse events.

All adverse events must be recorded in the subject's source documents and on the CRF regardless of frequency, severity (grade) or assessed relationship to therapy. Additionally, SAEs must be submitted to the Safety vendor within 24 hours of awareness.

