## **11.5. Follow-up of AEs and SAEs**

If an adverse event changes in severity grade between the date it was initially recorded through the 30-Day Follow-up Period, the event should be recorded as a new AE; however, only one SAE should be reported to the Safety vendor for the event with the highest severity grade recorded.

After the initial AE/SAE report, the Investigator is required to proactively follow each subject and provide further information on the subject's condition. The Investigator will ensure that follow-up includes any supplemental investigations as may be indicated to elucidate the nature and/or causality of the AE or SAE. This may include additional laboratory tests or investigations, histopathological examinations, or consultation with other health care professionals.

Non-serious AEs that have not resolved within 30 days after last dose of GC4419 will be considered ongoing, and marked as such in the CRF. All SAEs will be followed until they resolve or a new baseline is established, at which point the appropriate CRF page(s) or SAE Report Form(s) will be updated.

Routine collection of AEs will stop 30 days after last dose of GC4419, IMRT, or cisplatin (i.e., whichever occurs last); however, collection of clinical data will continue on events of interest or as clinical circumstances warrant that exceed the 30 days after last dose of GC4419, per below and described in other sections of the Protocol:

- OM: 4 weeks post last IMRT dose ([Section 10.7.3.1](#))
- Medical events which in the opinion of the Investigator, serious and are believed to be a result of study participation to warrant notifying the Sponsor ([Section 11.6](#) and [Section 11.8](#)). In these circumstances, the Investigator should contact the Galera Medical Monitor (or designee) directly to discuss the case, and how it should be reported.

As reasonably requested by the Sponsor, the Investigator will perform or arrange for the conduct of supplemental measurements and/or evaluations to elucidate as fully as possible the nature and/or causality of the AE or SAE. If a subject dies during participation in the study or during a 30-Day Follow-Up Period, the Sponsor will be provided with a copy of any post-mortem findings, including histopathology.

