## **15. DATA HANDLING AND RECORDKEEPING**

### **15.1. Case Report Forms**

All required study data must be recorded on the electronic CRF provided by the Sponsor or its representatives. The data recorded onto the electronic CRF is derived from the source documents. The Investigator shall ensure that all data in the electronic CRF is accurate and consistent with the source documents or that any discrepancies of the electronic CRF with source documents are explained (ICH-GCP 4.9.2).

Electronic case report forms will be accessed by the study center for collection of all study data, and a copy of the electronic CRF will be provided to the site for the Investigator files. For each subject, the electronic CRF must be completed by site staff and must be signed electronically by the Principal Investigator in a timely fashion after data collection. If a subject withdraws from the study, the electronic CRFs should be promptly completed and the reason for withdrawal must be noted. If a subject is withdrawn from the study because of a drug-related toxicity, thorough efforts should be made to clearly document the outcome.

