AEs and SAEs with onset dates on or after the date of enrollment through 30 days following the last dose of GC4419, IMRT or cisplatin (i.e. whichever occurs last) will be recorded on the CRF. All subjects with SAEs will be followed until the events resolve, stabilize, become chronic, the subject completes the study, or the subject is lost to follow-up.

 Ventricular rate and P-R, QRS, QT, and QTc intervals will be assessed and recorded at Screening.

All OM assessments must be performed by trained evaluators. The extent of the subject's OM will be scored using the WHO OM toxicity scale. OM assessments will be completed at the Screening Visit, at the Baseline Visit, twice weekly (no less than two days apart) within each 5-day IMRT period and on the last day of IMRT or Early Termination Visit. For Week 1, the first OM assessment will occur at the Baseline Visit and one additional OM assessment must occur at least two days later during the week. The extent of the subject's OM will be scored using the WHO OM toxicity scale. OM assessments should continue weekly for four weeks following the last day of IMRT (Day 7, Day 14, Day 21 and Day 28  $\pm 2$  calendar days).

Symptom Related Questionnaires to be completed by subjects prior to the OM assessment at W1D1, and then prior to the second OM assessment each week and 28 days ( $\pm 2$  calendar days) post end of treatment (EOT).

For a woman of childbearing potential, serum pregnancy test must be performed at the Screening Visit and at the Last Day of IMRT or Early Termination Visit.

Clinical laboratory measurements will be conducted at the Screening Visit, twice during Week 1 (once at the Baseline Visit and again on Day 3, 4 or 5), and once weekly from Week 2 through the last day of IMRT. Clinical laboratory measurements at these visits will include the hematology profile (hemoglobin, hematocrit, red blood cell count, white blood cell count with differential, and platelet count. Differential to include total neutrophils, lymphocytes, monocytes, eosinophils, and basophils) and chemistry profile (glucose, BUN, creatinine, sodium, potassium, calcium, albumin, total protein, total bilirubin, direct bilirubin, alkaline phosphatase, ALT (SGPT), AST (SGOT), chloride, phosphate, bicarbonate, magnesium).

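### Section 8.9 stops all data collection on complete removal from the study, even with consent intact, and so conflicts with the AE/SAE follow-up required by Sections 11.2.2, 11.5 and 15.1

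*Combined protocol and SAP*

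**What the plan says.** The stop rule is in Section 8.9 (Concomitant Medications). It applies "if a subject withdraws consent for the study or is removed from the study completely", explains complete removal as meaning that "the subject is no longer participating in any study procedures or follow-up", and concludes that "no further data should be collected after the date of the subject's study discontinuation".

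Three places allow removal without withdrawal of consent:

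- Section 7.6: "The Investigator may also, at his/her discretion, discontinue a subject from participating in this study at any time".
- Section 7.6 again: after therapy stops for an AE or SAE, the site must try to retain the subject, but may withdraw the subject if that fails.
- Section 8.9.1: after a prohibited medication, continuation in the study is decided case by case.

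Three places require data that the stop rule forbids:

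- Section 11.2.2: "AEs and SAEs will be followed for 30 days after the last dose of IMRT, cisplatin, or GC4419", whichever is last. New events that start in that window are also reportable.
- Section 11.5: "All SAEs will be followed until they resolve or a new baseline is established".
- Section 15.1: "If a subject is withdrawn from the study because of a drug-related toxicity, thorough efforts should be made to clearly document the outcome".

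The primary endpoint (Section 5.2) is the frequency, duration and severity of AEs and SAEs, plus laboratory abnormalities. Section 12.4 analyses safety in everyone who received at least one dose.

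**The concern.** Section 8.9 treats two different situations alike. A subject who withdraws consent may have closed the door on further data. A subject whom the investigator takes off study has not, and three other sections expect safety information from that subject. A site cannot follow all of them, and no text ranks them.

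At stake is the primary endpoint of a single-arm study without a data monitoring committee (Section 12.9). A removed subject stays in the denominator, while later events never reach the numerator and the recorded duration of ongoing events stops at removal. Removal can follow toxicity, so the loss can depend on the outcome being measured. Analysis cannot repair this. Section 12.5.2 lists missing-data topics for oral mucositis scores only, and no analysis rule restores events that were never collected.

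**Working it through.** **Step 1. The passages side by side, for a dosed subject removed completely with consent intact.**

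| Item | Section 8.9 | Other section |
|---|---|---|
| New AE or SAE within 30 days of the last treatment | Not collected | Reported (11.2.2); no exception for removed subjects |
| SAE ongoing at removal | Not collected | Followed to resolution or a new baseline (11.5); covers all SAEs |
| Outcome after withdrawal for drug-related toxicity | Not collected | Thorough efforts to document it (15.1); names withdrawn subjects |

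The conflict is most direct with Section 15.1, which assumes that a subject can be withdrawn from the study and still have an outcome recorded. Section 15.1 covers drug-related toxicity and outcome only, not the whole 30-day window. Section 11.2.2 conflicts because it has no exception.

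**Step 2. What one subject can lose.** In the example schedule of Table 2 the last treatment day is Day 47, so AE collection runs to Day 47 + 30 = 77. If a subject is removed completely on Day 22 and finishes IMRT/cisplatin off study, 77 − 22 = 55 days go uncollected, or 55/77 = 71%. This is one hypothetical subject, not an average.

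**Step 3. The plan's own figure.** Section 12.2 states a 95% probability that a 300-subject database shows at least one case of an AE with 1% true incidence: 1 − 0.99^300 = 0.9510. It reproduces. If k subjects contributed no event data, the probability becomes 1 − 0.99^(N − k). The values of k are assumptions:

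| k | N = 300 | N = 70 (this study alone) |
|---|---|---|
| 0 | 0.9510 | 0.5052 |
| 2 | 0.9500 | 0.4951 |
| 4 | 0.9489 | 0.4849 |
| 7 | 0.9474 | 0.4691 |
| 14 | 0.9435 | 0.4304 |

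Even at k = 14 the programme figure falls by 0.9510 − 0.9435 = 0.0075, under one percentage point. Section 12.2 counts only full-course subjects in the 300, so a subject removed mid-course would not be among them.

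**Step 4. Possible under-count in this study.** Let d be the share removed completely and r their AE risk relative to the others. Suppose all their events of a given type fall after removal, which is the extreme case. Then observed/true incidence = (1 − d) / [(1 − d) + d·r]. The documents give neither d nor r, so both are assumed:

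| d | Too low by, r = 1 | Too low by, r = 3 |
|---|---|---|
| 2% | 2% | 1 − 0.98/1.04 = 6% |
| 5% | 5% | 1 − 0.95/1.10 = 14% |
| 10% | 10% | 1 − 0.90/1.20 = 25% |
| 20% | 20% | 1 − 0.80/1.40 = 43% |

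These are relative reductions. They show direction and sensitivity and do not estimate what will happen.

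**The case against.** **The rule is narrow.** It needs complete removal, and stopping GC4419 alone does not trigger it. Section 9.1 keeps subjects who cannot tolerate the drug in study assessments, Section 7.6 tells sites to try to retain those who stop for an AE or SAE, and Section 8.9.1 says that a prohibited medication does not mean automatic removal. This stands: the affected group is residual. It is not empty, because discretionary removal needs no stated reason.

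**A subject still followed for an SAE is not completely removed.** On this reading the sections never meet. But nothing obliges an investigator who removes a subject to keep safety follow-up open, and Section 15.1 plainly contemplates outcomes in withdrawn subjects.

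**The sentence sits under concomitant medications and may concern only those data.** Its placement suggests so, but its wording covers data without limit and refers to all procedures and follow-up. A site could fairly read it either way.

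**Other text limits the loss.** Table 5 footnote 1 requires the last-day procedures when a subject ends early. Section 11.5 asks for post-mortem findings for deaths in the 30-day period, and for contact with the medical monitor about serious events attributed to participation. Section 11.6 allows later SAEs to be reported. This stands in part: total loss does not follow. But the first is a single visit, Section 11.6 permits reporting without seeking it, and the Section 11.5 provisions themselves sit uneasily with the stop rule.

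**Conclusion.** The contradiction is real and needs reconciling. For a dosed subject removed completely without withdrawing consent, Section 8.9 forbids data that Sections 11.2.2, 11.5 and 15.1 require. If sites follow Section 8.9, AEs and SAEs can be under-counted and their durations truncated in the primary endpoint. The direction rests on removed subjects staying in the all-dosed denominator. The size cannot be computed because no rate of complete removal is given. It is probably small, and the effect on the 300-subject detection target is under one point even if 14 subjects contributed nothing.

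A reader might infer more, but the documents do not support it:

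- *That the primary endpoint is biased by a known amount.* Bias is possible, not established.
- *That 7 to 14 subjects (10–20% of 70) cap the number affected.* The 10–20% in Section 12.2 is stopping GC4419 before 6 weeks. It includes people who stay on study and leaves out people removed later, so it is neither an estimate nor a bound.
- *That Section 7.7 is a further route to removing an individual.* It concerns suspension or closure of the study or a site.
- *That Table 5 footnote 10 is part of the same conflict.* It has SAEs "followed until the events resolve, stabilize, become chronic, the subject completes the study, or the subject is lost to follow-up". Removal is not on that list, so the mismatch with Section 11.5 is separate and smaller.

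**What to change.** In Section 8.9, limit the stop on data collection to subjects who withdraw consent for further data collection. State that for every other complete removal AE/SAE and vital-status collection continues through the 30-day window of Section 11.2.2, with telephone contact or chart review sufficient, and that SAEs are followed as in Section 11.5. Record on the CRF whether the subject stopped drug, visits or data collection.

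Separately, reconcile the end points for SAE follow-up in Table 5 footnote 10 with Section 11.5. Deleting study completion from the footnote would not be enough, because stabilisation, chronicity and loss to follow-up would still differ from resolution or a new baseline.

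The cost is a few sentences, one CRF field, and a call or chart check for what are likely to be few subjects. No visits or subjects are added.
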